6.1 Participant Screening

Inclusion Criteria

- Walking speed <0.8m/s
- Self-reported Physical activity <3 hours/week
- Hand grip strength <30 kgs for men & <20 kgs for women (this will be assessed only for participants who come for in-person assessment)
- Not on any sedative drugs
- Can understand & communicate in English
- Ability to walk more than 30 feet with or without an assistive device
- Must have either a desktop computer/laptop/tablet with access to internet (only for participants who choose to go for online assessments and/or training)Must have a helper buddy assistance (only for participants who choose to go for online assessments and/or training). The helper buddy will be asked to stay in the same room throughout the online assessment and online training sessions. The helper buddy will not participate in any other way throughout the research procedures. In case of any adverse event, we will follow the adverse event protocol. The session will be immediately concluded, and the participant will be provided all the necessary support by the helper buddy while the research personnel stays online to ensure the participant is taken care of. The participant will be asked for symptoms and the type of discomfort he/she is experiencing. The adverse event will be immediately reported to the PI and the participant will be asked to visit his physician or doctor to seek medical attention in case the symptoms persist for more than a day. In case of emergency, like chest discomfort, the helper buddy will be asked to call 911 immediately
- 2-minute step in place test or walk around: The participant is asked to stand up straight next to the wall with the heart rate/O2 monitor plugged in to the index finger. The subject then marches in place or walks around the room (with health coach able to see them on the screen) for two minutes. On completion, the health coach will obtain the heart rate and oxygen saturation. If the HR exceeds 85% of age appropriate HR max and O2 saturation falls below 90% then they will be excluded from the study.

Exclusion Criteria

- Participants will not proceed with the study if any of the following occurs at baseline measurement: 1) HR > 85% of age-predicted maximal heart rate (HRmax) (HRmax = 220 age), 2) systolic blood pressure (SBP) > 165 mmHg and/or diastolic blood pressure (DBP) > 110 mmHg during resting), and/or 3) oxygen saturation (measured by pulse oximeter) during resting < 90% (only for participants who choose to go for inperson assessment and/or training). For The blood pressure criteria is only for participants who choose to go for in-person assessment and/or training which will be measured in laboratory (Group 1 and 2). To serve good for safety in group 3 (online assessment and online training), we will mail O₂ saturation monitors along with heart rate monitors. Participants will not proceed with the study if at baseline measurement HR > 85% of age-predicted maximal heart rate (HRmax) (HRmax = 220 age) (only for participants who choose to go for online assessments and/or training). If excluded and the participant wants to participate in the study, they would need to obtain a physician consent.
- Unable to stand for 5 minutes without an assistive device (length of a Wii Fit game)
- Uncontrolled acute medical/surgical, neurological or cardiovascular disease
- History of bone fracture or significant other systemic disease or surgery in the last six months
- Moderate to severe cognitive impairment (MOCA <24/30)
- Specific to MRI participants: Self-reported presence of pacemaker, metal implants other than orthopedic implants, and/or Claustrophobia, cataract surgery (lens not compatible to the MRI confirmed by the MRI technician)
- Do not have either a desktop computer/laptop/tablet with access to internet (only for participants who choose to go for online assessments and/or training)
- Do not have a helper buddy to assist or provide physical support (only for participants who choose to go for online assessments and/or training)
- Participants who cannot understand and communicate in English will be excluded due to instructions for training and protocol being provided in English.

6.2 Intervention

Group A – CogXergaming

[For Group 1(in-person assessments and in-person training)]

CogXergaming based cognitive-motor balance training will be delivered to group A using the commercially available Wii-Fit Nintendo and a mouse in conjunction with cognitive training. All participants will undergo 18 sessions of training in a tapering manner for six weeks with 60-90 minutes of training per session, i.e., 3 sessions each week till the 6th week. Each session will be divided into 3 sub-sessions, where each sub-session will consist of playing 4 to 6 games in conjunction with cognitive task. All the games will be performed using a Wii-Fit balance board in front of a TV screen. At the beginning of each session, 10 minutes of warm exercises will be provided that includes self-stretches, lunges, squats, high stepping and chair rises. The participant

will play four of the six balance board games Table tilt, Tightrope, Soccer, Balance bubble, Light Run and Basic Step (each game is max 1.5 minutes). The Light Run and Basic Step is a challenging game which will be replaced by any of the 2 games aced for 2 consecutive sessions. Each game will be superimposed with any 3 of the 6 cognitive tasks (word list generation consisting of verbal fluency (VF) and category fluency (CF), digit recall (DR), analogies (AN), mental arithmetic (MA), repeated letter (RL). In the VF and CF task, Participants will be asked to recite as many words as they can, from a given category or an alphabet (e.g., participants will be asked to say as many names of "animals", "fruits" or words from a given alphabet letter, such as "S"). In the digit recall task, the participant will require to repeat the digits the research personnel told (e.g., please repeat the digits 153, and the participant is expected recite the 3 digits). Participants will be asked to respond to analogies asked, e.g., "Bird is to fly, and fish is to ". In the mental arithmetic task, the participant will be asked to mentally calculate and provide an answer to the math equation given, e.g., 4+2=? the participant is expected to reply "6". In the repeated letter task, the participant is simply asked to repeat only a specific letter and not repeat all the letter, e.g., please repeat the letter "A" only when you hear me say "A" and ignore all the others, the personnel will start saying a series of letter- B N O A, and the participant is expected to respond "A". The cognitive tasks will be randomized making sure that all the cognitive tasks are played with all the games. The cognitive and balance board game scores will be noted on the scoring sheet for each session. The cognitive and physical demand will be assessed after each game in the sub-session across the 12 sessions via NASA TLX [32]. The NASA TLX scores will be collected on an iPad/iPhone using the NASA TLX application and the data will be exported in the form of .csv file. Participants will be asked to rate their level of exertion on the Borg scale after each sub-session to determine the fatigue level of the training [33]. Blood pressure (BP) and heart rate (HR) will also be monitored prior to and after each sub-session. A total 10 minutes rest interval between every sub-session will be mandatorily provided. In case of any fatigue noticed or the participant demands a break, they will be seated back in a chair and their vitals will be monitored to ensure safety. The rest intervals will be used to obtain HR and blood pressure for safety monitoring. The projected total time spent on intervention is estimated to be 60 minutes (10 minutes warm-up + 30 minutes Exergaming + 20 minutes break). A physical therapist will provide external assistance (contact guard support) or guided movements and monitor any adverse reactions (changes in perceived exertion, cardiovascular monitoring etc.). All participants' compliance will be calculated at the end of the 6 weeks of training.

Group A – CogXergaming in the form of TeleXercise intervention
[For Group 2 (in-person assessments and online training) & Group 3 (online assessments and online training)]

The TeleXercise intervention proposes to deliver exercises via exergaming-based animation videos combined with or without explicit cognitive exercises delivered by a research personnel monitoring the intervention. All the online training sessions will be carried out on one-on-one basis. Participants will need a desktop computer/tablet or smart phone of their own with access to internet on which the commercially available application will be installed. Research personnel will set up meeting invites and send them links via their preferred receiving mode (SMS or email). Once the research personnel admits all participants into the room via the secure link the research personnel will start the intervention. The research personnel will launch the Mimic-Game-&-Groove application on their computer and share their screen with the participants. Participants have to turn their videos on for the research personnel to see them. The audio will be kept in mute by the health coach and once the participant tries to talk or show any discomfort he/she will unmute in any unanticipated event. The intervention consists of participants mimicking the exercises that are shown in form of games and dances on their screen (similar to exergaming but being passive rather than interactive). The participants will not receive knowledge of performance or knowledge of results like in traditional exergaming; however, after each session, they will receive a brief feedback by the health coach, 1) qualitative based on the movements, 2) quantitative based on their heart rate max (intensity achieved) and the number of steps per session (measured via wearable sensors/smartphone). Participants will receive the TeleXercise intervention for three times per week for 6 weeks (18 sessions) with each session lasting about 1 hour and 30 minutes, including warm-ups, rests, and a cooldown. Training will consist of 20 minutes of warm-up -joint mobility, walking, and stretching exercises of moderate intensity, and cool-down- low-intensity stretching exercises and 1 hour of TeleXercise. A wearable device provided will measure the heart rate and physical activity during the course of training. They will be asked to read out the Heart rate and number of steps before the training begins (which will be displayed on the wearable device). Furthermore, after each set of exercise, they will be asked to note down their heart rate and number of steps displayed on their watch and when asked they should report it to the research personnel. Participants must be below 85% of the age predicted maximum heart rate to continue testing and training. All participants will be provided with a feasibility questionnaire and their compliance will be recorded at the end of the 4 weeks of training. Participants are provided with a set of balance exercises, which are demonstrated via animated avatars. The balance exercises includes non-interactive balance games (stepping forward, backward, sideways), Tai-Chi, Weight shifting (to right leg, left leg and practice distributing equal weights on both the legs), Aerobic (stepping in place), dance, strength, and stretching. Please see the figure below

DASH BOARD

[figure not shown]

Figure 1.

Each game will be superimposed with any 3 of the 6 cognitive tasks (word list generation consisting of verbal fluency (VF) and category fluency (CF), digit recall (DR), analogies (AN), mental arithmetic (MA), repeated letter (RL). In the VF and CF task, subjects will be asked to recite as many words as they can, from a given category or an alphabet (e.g., participants will be asked to say as many names of "animals", "fruits" or words from a given alphabet letter, such as "S"). In the digit recall task, the participant will require to repeat the digits the research personnel told (e.g., please repeat the digits 153, and the participant is expected recite the 3 digits). Participants will be asked to respond to analogies asked, e.g., "Bird is to fly and fish is to". In the mental arithmetic task, the participant will be asked to mentally calculate and provide an answer to the math equation given, e.g., 4+2=?, the participant is expected to reply 6. In the repeated letter task, the participant is simply asked to repeat only a specific letter and not repeat all the letter, e.g., please repeat the letter "A" only when you hear me say "A" and ignore all the others, the personnel will start saying a series of letters- B N O A. and the participant is expected to respond "A". The cognitive tasks will be randomized making sure that all the cognitive tasks are played with all the games. The cognitive and physical demand will be assessed after each game via NASA TLX (20,21). The NASA TLX is a numerical 20 point-scale and participants will respond to the cognitive and physical demand questions accordingly. Participants will be asked to rate their level of exertion on the Borg CR10 scale to determine the fatigue level of the training (22,23). In case of any fatigue noticed or the participant demands a break, they will be asked to sit back in a chair and they will be asked to monitor their vitals and report to the remote research personnel to ensure safety. All participants compliance will be calculated across the training sessions

Group B – Matter of Balance training [For Group 1(in-person assessments and in-person training) and Online version for Group 2(in-person assessments and online training), Group 3(online assessments and online training)]

Participants will undergo matter of balance training for 8 weeks (one session a week for 2 hours/day). The program emphasizes practical coping strategies that include group discussions, mutual problem solving, exercises to improve strength, coordination and balance, and a home safety evaluation. The program will be offered by graduate and post-doc research associates in the UIC Physical Therapy Department who will be certified A Matter of Balance (AMOB) coaches. The details of the exercise intervention are provided in the manual attached. Similar intervention for AMOB training will be provided online for participants in Group 2 and Group 3. All the online training sessions will be carried out on 1-on-1 basis.

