6.4 Outcomes

Assessment: The following tests will be administered as baseline and post-intervention. Table 1: Assessment variables for Groups 1 and 2 (In-person assessment) and Group 3 (Online-assessment)

| Group 1 and 2 Assessments (In-person assessment) | Group 3 Assessments (Online Assessment) | | | | | | |
|--|---|--|--|--|--|--|--|
| Balance Intentional balance control (Limits of stability test) (single and Dual task conditions) Postural control (sensory organization test) (single and Dual task conditions) Reactive balance control (Stance perturbation test) (single and Dual task conditions) NIH balance Toolbox (Standing balance test) Gait GaitRite mat (single and Dual task conditions) NIH Balance toolbox (4m walk Gait speed test) | Balance - 30-second chair stand test - Four-step square test - Sharpened Romberg's - One leg stance test Gait - Tinetti Performance Oriented Mobility Assessment | | | | | | |
| Muscular fitness - Isokinetic Dynamometer - B-mode Ultrasonography Cardiovascular fitness - Heart rate variability - YMCA submaximal cycle Ergometer test - NIH Balance toolbox (2-minute walk endurance test) | Cardiovascular fitness - 2-minute step in place test | | | | | | |
| Cognitive performance - Neuropsychological battery tests - NIH cognitive toolbox - Auditory clock test and letter number sequencing (single and Dual task conditions) Physical activity and motivation - Smartphone (Android/iphone) | Cognitive performance - Neuropsychological battery tests - NIH cognitive toolbox - Auditory clock test and letter number sequencing (single and Dual task conditions) Physical activity and motivation - Smartphone (Android/iphone) | | | | | | |

| fMRI scanning | - |
|---|---|
| - Intrinsic motivational index | - Intrinsic motivational index |
| - Physical activity scale for the elderly | - Physical activity scale for the elderly |
| - Quality of life (SF-36) | - Quality of life (SF-36) |
| - Wearable sensor | - Wearable sensor |
| | |

Aim 1: Balance and Gait tests:

Balance:

For In-Person Assessment (Group 1 and 2)

Intentional balance control

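### Group 1 arm A trains verbal and category fluency, which are also outcome tests, so a between-arm difference on these 2 of 14 in-person cognitive tests cannot by itself show better global cognition

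*Combined protocol and SAP*

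**What the plan says.** **Training, arm A in person.** Section 6.2 lays three of six cognitive tasks over each game. The list begins with "word list generation consisting of verbal fluency (VF) and category fluency (CF), digit recall (DR" and continues with analogies, mental arithmetic and repeated letter. The example fluency cues are animals, fruits and the letter S. On volume, "each sub-session will consist of playing 4 to 6 games in conjunction with cognitive task", and the session budget is "10 minutes warm-up + 30 minutes Exergaming + 20 minutes break".

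**Training, arm A online.** The TeleXercise text in section 6.2 first describes videos "combined with or without explicit cognitive exercises delivered by a research personnel monitoring the intervention". It later lays the same six tasks over every game, and for fluency says "subjects will be asked to recite as many words as they can, from a given category or an alphabet".

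**Training, arm B.** Matter of Balance covers "group discussions, mutual problem solving, exercises to improve strength, coordination and balance, and a home safety evaluation". No fluency task is described. However, "The details of the exercise intervention are provided in the manual attached", and that manual is not part of the text.

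**Outcomes.** Section 6.4 introduces the assessments with "The following tests will be administered as baseline and post-intervention". Under Cognitive Function for Groups 1 and 2, category fluency and verbal fluency are tests 2 and 3 of the seven-test neuropsychological battery. The example cues are animals, boys' names and fruits, and the letter A. For Group 3, Table 1 lists the battery, but the online test descriptions that follow contain no fluency test.

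**Claim and analysis.** Aim 1 in section 3.0 expects arm A to beat arm B on global cognition. Section 12.0 examines pre-post changes in the cognitive measures by ANCOVA. Nothing in the documents marks the fluency tests as trained, keeps test cues out of training, or defines which tests make up global cognition.

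**The concern.** In training and in testing the participant does the same thing: say as many words as possible from a category or a letter. If only one arm rehearses this for six weeks, a better fluency score in that arm has two readings. It may show a broader cognitive benefit, which is what Aim 1 claims, or it may show practice on that task.

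The stake is the interpretation of part of the cognition result. No rule says which cognitive tests carry the global-cognition claim, so a fluency result could be cited for it. Section 12.0 also intends the data to inform a power analysis for a larger trial. A fluency effect used there without a label would carry the same ambiguity, although the documents do not say that fluency will be the measure used.

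**Working it through.** **1. Who is exposed**

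| Group | Fluency trained in arm A? | Fluency tested? |
|---|---|---|
| 1 | Yes (section 6.2, in person) | Yes (section 6.4) |
| 2 | Only if the every-game text governs over the with-or-without text | Yes (section 6.4) |
| 3 | Same condition as Group 2 | Only if Table 1 governs over the online test descriptions |

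**2. Share of the cognitive tests (Groups 1 and 2), counting each named test once**

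- Battery 7 + NIH toolbox 5 + auditory clock 1 + letter-number sequencing 1 = 14.
- Trained: 2 of 14 = 14.3%. Within the battery, 2 of 7 = 28.6%. Within the NIH toolbox, 0 of 5.
- Not listed as training tasks: 14 − 2 = 12. Counting single- and dual-task versions separately would enlarge the denominator.

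**3. Planned exposure in Group 1A at full attendance**

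Inputs from section 6.2: 18 sessions, 3 sub-sessions, 4 to 6 games per sub-session, 3 of 6 tasks per game, at most 1.5 minutes per game. Assumptions: the six tasks rotate equally, and the three tasks in a game take equal turns of 1.5 / 3 = 0.5 minutes.

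- Games: 18 × 3 × 4 = 216; 18 × 3 × 6 = 324.
- Games per fluency task: 216 × 3/6 = 108; 324 × 3/6 = 162.
- Minutes per fluency task: 108 × 0.5 = 54; 162 × 0.5 = 81.

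The 30 minutes of exergaming per session would give 18 × 30 / 6 = 90 minutes per task. That exceeds the ceiling on play, since 3 × 6 × 1.5 = 27 minutes per session. Section 7.0 allows about 10 minutes for four games whose play lasts at most 4 × 1.5 = 6 minutes, so the 30 minutes is not all play. The upper figure is therefore 81.

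**4. Why ANCOVA does not settle it**

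Write post-test score = a + b × baseline + (δ + π) × arm + error, where δ is a broader cognitive benefit and π is gain from practising the task. Baseline is measured before training, so adjusting for it leaves π in the arm coefficient. The data from these two tests estimate δ + π only.

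**5. Illustration of how much it could matter**

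The plan's sample-size figures reproduce: 120 × 0.8 = 96 and 96 / 6 = 16, so Groups 1 and 2 together give 2 × 16 = 32 per arm. The documents state no alpha, SD or practice effect. Assume two-sided 0.05, δ = 0, and a practice effect of d standard deviations averaged over the 32.

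- Chance of a significant result favouring A on one fluency test: Φ(d × √(32/2) − 1.96) = Φ(4d − 1.96).
- Shift in an equal-weight mean of 14 z-scores: 2d/14. Dividing by √((1 + 13r)/14), where r is the correlation between tests, gives the standardised effect.

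| d (assumed) | One fluency test | Shift in 14-test mean | Standardised, r = 0 / 0.3 / 0.7 |
|---|---|---|---|
| 0.2 | 12% | 0.03 | 0.107 / 0.048 / 0.034 |
| 0.5 | 52% | 0.07 | 0.267 / 0.121 / 0.084 |
| 0.8 | 89% | 0.11 | 0.428 / 0.193 / 0.135 |

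If only Group 1A is exposed, d in the pooled comparison is half its Group 1 value (16 of 32). The table shows that the consequence depends on whether fluency is read alone or as part of a wide average. It does not estimate the bias in this trial.

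**The case against.** The strongest reply is that fluency is a declared part of a cognitive-motor programme, so testing it is a legitimate proximal outcome and a gain may be exactly what was intended. That stands. It makes fluency evidence that the trained skill improved, which is less than evidence of better global cognition.

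A second reply is that little rests on two tests. Section 6.4 assigns the NIH toolbox the role of determining change in cognitive function, none of its five tests is a listed training task, and a 14-test average would move little. This also stands, and it limits the point. But the plan does not specify such an average or name a deciding cognitive test, so nothing stops fluency being cited alone.

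Third, carry-over is uncertain. Training takes place during balance games, whereas testing uses headphones and a microphone. The cues are examples only, and the example letters differ. The arm B manual might contain something comparable. All of this is fair, and it is why the point says that a difference could reflect practice.

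A reader might go further and infer that test items are drilled in arm A, or that the whole A-versus-B cognition comparison is invalid. The documents do not support either reading. The shared categories are illustrations, so actual item overlap is unknown, and 12 of the 14 tests are not listed training tasks.

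**Conclusion.** The point holds within limits. For Group 1, a between-arm difference on verbal or category fluency could reflect practice in one arm and cannot by itself support the Aim 1 claim of better global cognition. It affects 2 of 14 in-person cognitive tests, so Aim 1 is partly exposed. It does not threaten the trial, but it should be settled before analysis because settling it is cheap.

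The exposure figures (108 to 162 games and at most about 54 to 81 minutes per fluency task) rest on full attendance, equal rotation and turn-taking, none of which the text fixes. They measure planned exposure and say nothing about the size of any gain, so no false-positive rate is claimed. That only one arm practises rests on the description of arm B without its manual.

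It would be tempting to say that all three groups are affected. The documents do not establish that: Group 2 depends on one unresolved conflict in the text, and Group 3 on two.

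**What to change.** 1. In section 12.0, name verbal and category fluency as trained tasks in arm A and report them separately. Base the global-cognition comparison on untrained tests already collected, for example the five NIH toolbox tests.
2. In both arm A descriptions in section 6.2 and in the cognitive section of 6.4, state that the categories and letters used for testing are not used in training. This prevents rehearsal of the items but not practice of the task, so item 1 is still needed.
3. Reconcile the two TeleXercise statements in section 6.2 on whether the online sessions include the cognitive tasks. Reconcile Table 1 with the online test descriptions in section 6.4 on whether Group 3 takes the fluency tests. Until both are settled, the affected groups are not known.

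The cost is a few sentences and a training cue list that leaves out the test cues; no new data are needed. The downside is that fluency becomes supportive evidence only for the cognition claim.

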3.0 Objectives/Aims

Aim 1: To test the feasibility (compliance and effectiveness) of cognitive-motor exergaming (CogXergaming) in the frail older adults and to compare the improvements in behavioral biomarkers in this group across balance, muscle fitness, cardiovascular fitness and global cognition to the group receiving the Matter of Balance training.

Hypothesis: Participants will respond well to CogXergaming training paradigm and demonstrate significant improvements in balance, muscular fitness, cardiovascular fitness and global cognition as compared to the Matter of Balance training group.

Aim 2: To examine the effect of CogXergaming on physical activity levels and quality of life measures post-intervention.

Hypothesis: The participants who received CogXergaming will demonstrate significant improvement in physical activity and quality of life post-training as compared to their own pre-training scores.

Aim 3: To examine the effect of CogXergaming structural and functional connectivity within the cognitive-motor areas pre and post training to establish effect size.

Hypothesis: Post-training, participants will demonstrate improved memory consolidation, attention, motor planning and execution compared to pre-training indicating improved functional connectivity within the cognitive-motor areas.

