5.0 Subject Enrollment

A total of 120 participants will be enrolled in the pilot study (see Research Design and Procedures for details).

We will initially recruit the participants by posting flyers (approved by the Institutional Review Board) at Geriatric and internal medicine by contacting [name], giving presentations to potential participants at various exercise centers and senior homes. We will also use social media, such as Facebook, Twitter, etc. to post flyer for recruitment. As a part of recruitment procedure, we will not be accessing the EMRs, and will get referrals from different physicians for those who are potentially eligible to participate in our study. Our research staff team will travel to various locations to provide the background education about our study and explain the procedures through the study involved and will show them the consent form. The consent form will provide enough information about the study and the interested people will be asked to provide their contact information, which will be noted down on a sheet. Later, one of the researchers mentioned on the Appendix P will contact them for a telephone screening. Individuals making the initial contact looking at flyers will also undergo the same telephone screening question and will be asked where they heard/read about the study. The initial telephone screening would determine their general health condition, preliminary eligibility. They will be asked to choose a group that they prefer to participate which includes 3 options- 1) Group 1: In-person assessments and inperson training (where all the tests and training sessions will be conducted in the laboratory); 2) Group 2: In-person assessments and online training (where only the tests before and after training will be conducted in the laboratory and they

[figure not shown]

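### Section 6.2 gives inconsistent timing for Group A compliance: TeleXercise lasts 6 weeks, but one sentence records compliance and feasibility at the end of 4 weeks of training

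*Combined protocol and SAP*

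**What the plan says.** Section 3.0 makes compliance part of the first aim: "To test the feasibility (compliance and effectiveness) of cognitive-motor exergaming (CogXergaming) in the frail older adults".

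Section 6.2 describes two delivery modes for Group A, and both have 18 sessions over 6 weeks. For the online mode it states: "Participants will receive the TeleXercise intervention for three times per week for 6 weeks (18 sessions". This mode is headed "For Group 2 (in-person assessments and online training) & Group 3 (online assessments and online training", so it applies to Groups 2A and 3A. Section 6.0 gives the same 6 weeks and 18 sessions for Group A in all three preference groups.

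The timing of compliance then appears three times in Section 6.2:

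- In-person CogXergaming (Group 1A): "compliance will be calculated at the end of the 6 weeks of training".
- TeleXercise, in the sentence that also covers the feasibility questionnaire: "their compliance will be recorded at the end of the 4 weeks of training".
- TeleXercise, at the end of the same subsection: "All participants compliance will be calculated across the training sessions".

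No section gives a compliance formula, a denominator or a threshold. Section 12.0 does not mention compliance.

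**The concern.** The 4-week sentence is an operative instruction for an Aim 1 component, and it does not fit the length of the programme it belongs to. Staff who follow it would close the compliance record with a third of the programme still to run. As the sentence reads, they would also hand out the feasibility questionnaire then, so participants would judge a programme they had not finished. The questionnaire has no other stated time point.

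The later TeleXercise sentence does not remove the problem. It says how compliance is calculated but gives no end date or number of sessions. A team could record at week 4 under one sentence, calculate across the sessions recorded so far under the other, and believe it had followed both.

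What is at stake is the meaning of the compliance figure. A percentage from Groups 2A and 3A could rest on a different part of the programme from the percentage for Group 1A, and a reader of the report could not tell. Section 6.4 also links the motivation inventory to compliance and collects it after the intervention is completed. A week-4 compliance figure would not match it in time.

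**Working it through.** **Inputs**

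- Sessions per week and weeks of TeleXercise: 3 and 6 (Section 6.2).
- Literal recording point: end of week 4 (Section 6.2, TeleXercise).
- Enrolment: "A total of 120 participants will be enrolled in the pilot study" (Section 5.0).
- Attrition 20%, 96 evaluable, 16 in each of six subgroups (Section 12.0).

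**Reproducing the plan's own figures**

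- Sessions: 3 × 6 = 18, as stated.
- Evaluable: 120 × (1 − 0.20) = 96, and 96 / 6 = 16 per subgroup, as stated.

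**Sessions outside a 4-week window**

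- By week 4: 3 × 4 = 12.
- Left out: 18 − 12 = 6, and 6 / 18 = 33.3%.

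**Participants affected, if cells fill as planned**

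- Evaluable: arm A is 3 × 16 = 48; Groups 2A and 3A are 2 × 16 = 32; 32 / 48 = 66.7%.
- Enrolled: 120 / 6 = 20 per cell, so 40 of 60.

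**Effect on one participant's figure**

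The documents give no formula, so I assume sessions attended divided by sessions in the window. For someone who attends all of the first 12:

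| Attended of last 6 | Read at week 4 | Over 18 sessions |
|---|---|---|
| 0 | 12/12 = 100% | 12/18 = 66.7% |
| 2 | 100% | 14/18 = 77.8% |
| 4 | 100% | 16/18 = 88.9% |
| 6 | 100% | 18/18 = 100% |

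The error can go the other way. Someone who attends none of the first 12 and all of the last 6 reads 0% at week 4 and 6/18 = 33.3% over the programme.

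In general, let p1 be the attendance rate in sessions 1–12 and p2 the rate in sessions 13–18. The week-4 figure is p1, and the full figure is (12·p1 + 6·p2) / 18. The difference is (p1 − p2) / 3. It is zero when attendance is level and at most 33.3 percentage points in either direction.

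**Effect on a group figure, from the plan's attrition alone**

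Assume that the 20% who are lost stay in the denominator and that attendance is otherwise complete. The gap is largest if all of them leave just after session 12: p1 = 1.00, p2 = 0.80, and (1.00 − 0.80) / 3 = 6.7 points, that is 100% against 93.3%. If they leave before the first session, p1 = p2 = 0.80 and the gap is zero. The documents do not say when attrition is expected, so the range is 0 to 6.7 points under these assumptions.

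**The case against.** The strongest reply is that this is one wrong number and not a measurement window. The sentence refers to the 4 weeks of training as if that were the whole programme, and its form mirrors the in-person sentence with 6 weeks. The same subsection ends by taking compliance across the training sessions. On that reading no session was ever meant to be dropped. This is a plausible reading and the documents do not rule it out. They do not establish it either, and the 4-week sentence remains the only timing given for the questionnaire.

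Several stronger conclusions are tempting, and the documents do not support them:

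- A reader might infer that the feasibility result will omit sessions 13 to 18. No section excludes them; omission follows only if the 4-week sentence is applied literally.
- A reader might infer that online compliance will be overstated because attendance tends to fall late. The documents give no attendance pattern by week, and the formula above shows that the error can have either sign.
- A reader might say that the denominators are 12 online and 18 in person. No denominator is stated for either mode.
- A reader might treat two thirds of arm A as fixed. Participants choose Group 1, 2 or 3 and a coin flip then assigns the arm (Section 6.0), so it is only a planning share.
- A reader might take the NASA TLX wording, "across the 12 sessions via NASA TLX", as evidence of a deliberate 12-session window. It concerns workload and stands only in the in-person text. It does not say which 12 sessions are meant, and the same paragraph puts compliance at 6 weeks. It is a separate inconsistency.

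It is also fair to say that no comparison of compliance between delivery modes is planned, so no planned test is invalidated. The per-session records described in Sections 6.2 and 8.0 might allow attendance to be reconstructed, although no attendance log is described.

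**Conclusion.** The inconsistency is real and should be corrected. Section 6.2 gives three timing statements for compliance in Group A, two of them inside the TeleXercise subsection, and nothing elsewhere says which governs. The loss is conditional. Read literally, the 4-week sentence leaves up to 6 of 18 sessions (33%) uncounted in Groups 2A and 3A, and a participant who stops after session 12 shows 100% instead of 67%. Under the sentence that closes the TeleXercise text, nothing is lost. The share affected, 32 of 48 evaluable arm A participants, assumes that cells fill as planned. The individual percentages assume a simple attended-over-scheduled definition, which the plan does not state. This is a small flaw in wording, but it bears on a named component of Aim 1.

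**What to change.** In the TeleXercise part of Section 6.2, change the time point for recording compliance and giving the feasibility questionnaire from 4 weeks to the end of the 6 weeks of training. State one definition for Groups 1A, 2A and 3A: sessions attended divided by 18. Record attendance explicitly for each session so that the figure does not depend on reconstruction from heart-rate, step or score sheets.

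Separately, reconcile the 12 sessions named for NASA TLX in the in-person text with the 18 sessions set at the start of that text, and say which sessions are rated.

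The change concerns measurement only and leaves the training as described. It costs a short protocol edit and a matching line on the training sheet. The one downside is that reported online compliance may come out slightly less favourable than a week-4 figure, if attendance is lower in the last 6 sessions.
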